	3.13.	5. Subject Satisfaction	16
2	3.14.	Endpoints	16
•	3.14.	1. Primary Endpoints	16
751		, "r · ···	-

ZELTIQ P/N: Protocol Number: ZA16-005

Part Number:	Revision: 01	Page 3 of 28	
Title: DualSculpting th	e Upper Arms Using Vacuu	m Applicators and a	
Customized Treatment Approach			

	3.14.2	2. Other Assessments	16
	3.15. 3.15.2 3.15.2 3.2 3.2 3.2	Statistical Analysis Plan * 2. Analysis Population * 3. Endpoint Analysis * 15.3.1. Primary Safety Endpoint: * 15.3.2. Primary Efficacy Endpoint: Photographic Evaluation * 15.3.3. Other Assessments: *	16 17 17 17 17
	3.16.	Protocol Adherence	18
	3.17.	Adverse Events	18
	3.18.	Reportable Incidents	20
4.	Stud	ly Management and Ouality Control	20
	4.1	Study Data Collection	20
	л. Л Э	Confidentiality	-• >∩
	4.2.		-0
	4.3.	Investigator Responsibilities	20
	4.3.1.	Investigator Pecords	20 21
	4.3.2.	Investigator Reports	22
	4.4	Snonson Desnonsibilities	 >>
	4.4.	Sponsor Responsibilities	2 3
	4.4.1.	Training	20
	443	Monitoring	24
	4.4.4.	Final Report	24
	4.4.5.	. Trial Registration	25
5.	Data	a Ownership	25
6.	Pub	lication Policy	25
7		/Develop for Area develop) E
/.	KISK	deneju Anuiysis	:0
	7.1.	Benefits	25
	7.2.	Risks	25

Part Number:	Revision: 01	Page 4 of 28
Title: DualScu	Ipting the Upper Arms Using Vacuum App	licators and a
Customized T	reatment Approach	

1. Protocol Summary

Title	DualSculpting the Upper Arms Using Vacuum Applicators and a Customized Treatment Approach	
Design	Single-center, prospective, non-randomized, interventional cohort	
Purpose	Evaluate the safety and efficacy of the ZELTIQ CoolSculpting System using specialized vacuum applicators for non-invasive subcutaneous fat reduction of the upper arms.	
Enrollment	Up to 15 subjects enrolled	
Clinical Sites	One investigational site	
Subject population	Healthy adult women and men with clearly visible fat on the upper arms that they wish to have reduced	
Primary Endpoints	 Safety endpoint: The primary safety endpoint is the rate of unanticipated adverse device effects (UADE). It is expected there will be zero UADEs. Effectiveness endpoint: Correct identification of pre-treatment vs. 12-week post-final treatment images by at least two out of three blinded, independent reviewers. Success will be defined as at least 70% correct identification of the pre-treatment images. 	
Additional Assessments	 Subject satisfaction as assessed by questionnaire administered at 12 weeks post-final treatment. Assessment of fat reduction using various methods, which may include; ultrasound, caliper and circumference measurements. 	
Sponsor	ZELTIQ Aesthetics, Inc. [name]	

Part Number: Revision: 01 Page 5 of 28 Title: DualSculpting the Upper Arms Using Vacuum Applicators and a Customized Treatment Approach

2. Introduction

2.1.Background

Fat reduction and body contouring procedures, which include invasive, minimallyinvasive, and non-invasive procedures, have become increasingly popular aesthetic procedures. Patients who are obese and do not have specific fat bulges but require significant fat reduction to achieve aesthetic results are candidates for invasive and minimally-invasive procedures, such as liposuction and laser-assisted liposuction. Although effective at reducing fat, these invasive and minimally-invasive procedures involve significant patient pain, expense, downtime, and the risks typically associated with surgical procedures. As a result, patients who do not require significant fat reduction to achieve meaningful aesthetic results typically seek non-invasive fat reduction and body contouring procedures to avoid the pain, expense, downtime, and surgical risks associated with invasive and minimally-invasive procedures.

ZELTIQ Aesthetics has developed and commercialized a technology to non-invasively reduce subcutaneous fat. The ZELTIQ technology utilizes the sensitivity of fat cells to cold injury in order to selectively eliminate subcutaneous fat tissue without affecting the skin or other surrounding tissues. Termed cryolipolysis, this technology enables a non-invasive alternative for subcutaneous fat reduction through cellular apoptosis.

The purpose of this study is to evaluate the safety and efficacy of the ZELTIQ CoolSculpting System using vacuum applicators for non-invasive subcutaneous fat reduction in the upper arms. **Security of the security of the s**

2.2. Device Description

The study treatments will be performed using the ZELTIQ CoolSculpting System.

ZELTIQ P/N: Protocol Number: ZA16-005

Part Number:Revision: 01Page 6 of 28Title: DualSculpting the Upper Arms Using Vacuum Applicators and aCustomized Treatment Approach

This study will evaluate the safety and efficacy of the vacuum applicators to treat the upper arms. The subjects will receive bilateral treatment.

At the

investigator's discretion, an additional cooling cycle may be delivered to cover the treatment area (up to two cycles per each upper arm).

Figure 1: Cleared ZELTIQ System control unit.

Figure 2: Representation of Upper Arm Applicator

ZELTIQ P/N: Protocol Number: ZA16-005

Part Number: Revision: 01 Page 7 of 28 Title: DualSculpting the Upper Arms Using Vacuum Applicators and a Customized Treatment Approach

2.3. Regulatory Status

In Canada, the ZELTIQ CoolSculpting System is licensed (License #78510) and approved for:

- Fat layer reduction through cold-assisted lipolysis
- Minimizing pain and thermal injury during laser and dermatological treatments
- Acting as a local anesthetic for procedures that induce minor local discomfort

The ZELTIQ System can also provide localized thermal therapy (hot or cold) to minimize pain for post-traumatic and/or post-surgical pain and to temporarily relieve minor aches and pains and muscle spasms. The optional massage function can also be used for temporary:

- Relief of minor muscle aches, pain, and spasm
- Improvement in local circulation

The CoolSculpting System also received Health Canada approval in September 2015 for colder temperatures and shorter treatment times.

3. Study Protocol

3.1.Design

Prospective, non-randomized interventional cohort.

3.2. Study Duration

Enrollment and follow-up is expected to take up to five (5) months for each subject.

3.3. Physician Participants

Study investigators must be practicing medical physicians with experience in body contouring treatments.

3.4. Site Requirements

Study investigators must have at least one study coordinator with experience in conducting aesthetic research and with sufficient time to conduct the study.

Part Number: Revision: 01 Page 8 of 28 Title: DualSculpting the Upper Arms Using Vacuum Applicators and a Customized Treatment Approach

3.5.Subject Recruitment

Subjects who seek reduction of fat in the upper arm will be recruited from the general population.

3.6. Sample Size

A maximum of fifteen (15) subjects will be treated at one investigational site.

3.7. Patient Eligibility

To be eligible to participate, subjects must meet all of the inclusion criteria and none of the exclusion criteria listed in **Table 1**.

Table 1. Eligibility criteria.

Inclusion Criteria

- a) Male or female subjects ≥ 22 years of age and ≤ 65 years of age.
- b) Subject has clearly visible fat sufficient for treatment on the upper arm, which in the investigator's opinion, may benefit from the treatment.
- c) No weight change exceeding 5% in the preceding month.
- d) Subject agrees to maintain his/her weight (i.e., within 5% of total body weight) by not making any major changes in their diet or exercise routine during the course of the study.
- e) Subject has read and signed the study written informed consent form.

Exclusion Criteria

- a) History of a fat reduction procedure (e.g., liposuction, surgery, lipolytic agents, etc.), or implants in or adjacent to the area of intended treatment.
- b) History of prior surgery in the arms.
- c) Known history of cryoglobulinemia, cold urticaria, cold agglutinin disease, or paroxysmal cold hemoglobinuria.
- d) Known history of Raynaud's disease, or any known condition with a response to cold exposure that limits blood flow to the skin.
- e) History of bleeding disorder or is taking any medication that in the investigator's opinion may increase the subject's risk of bruising.
- f) History of carpal tunnel syndrome, compartment syndrome or deep vein thrombosis in the upper extremities.
- g) Currently taking or has taken diet pills or weight control supplements within the past month.
- h) Any dermatological conditions, such as scars, infection, in the location of the treatment area that may interfere with the treatment or evaluation.
- i) Active implanted device such as a pacemaker, defibrillator, or drug delivery system.
- j) Pregnant or intending to become pregnant in the next 5 months.

ZELTIQ P/N:

Part Number: Revision: 01 Page 9 of 28 Title: DualSculpting the Upper Arms Using Vacuum Applicators and a Customized Treatment Approach

- k) Lactating or has been lactating in the past 6 months.
- 1) Unable or unwilling to comply with the study requirements.
- m) Currently enrolled in a clinical study of any other unapproved investigational drug or device. Any other condition or laboratory value that would, in the professional opinion of the investigator, potentially affect the subject's response or the integrity of the data or would pose an unacceptable risk to the subject.

3.8. Informed Consent

Study candidates shall receive an explanation of the study objectives, possible risks and benefits of the study, and be given adequate time to read the information included in the informed consent document. Candidates will be given an opportunity to ask questions about any of the information contained in the informed consent. Candidates must verbally acknowledge understanding of the informed consent, and sign the consent form accordingly. This form must have prior approval of the Institutional Review Board.

3.9. Screening Procedures

3.9.1. Screening Visit; Required; Day -60 to Day 0

All subjects screened for the study must be documented on the Screening Log.

After the informed consent is signed, subjects will be screened for eligibility. Each subject will be evaluated to determine that all eligibility criteria are met. The investigator or designee shall complete a brief medical history and examine the subject to confirm eligibility for the study.

- 1. Obtain height and weight.
- 2. Obtain measurement of upper arm length, distance from peak of bulge to elbow, and circumference at peak of bulge. (Optional)
- 3. Visually assess and palpate the intended treatment area to determine if it is appropriate for treatment.
- 4. Assess for dermatological conditions that may lead to exclusion of a subject from the study.
- 5. Obtain photos of both right and left arms. (Optional)
- 6. Document potential candidate's medication use (including over-thecounter medications, vitamins and herbs), Fitzpatrick Skin Type, and ethnicity as well as any skin irregularities (e.g. moles, birth marks, scars, stretch marks, discoloration) at the intended treatment area.

ZELTIQ P/N: Protocol Number: ZA16-005

Part Number:Revision: 01Page 10 of 28Title: DualSculpting the Upper Arms Using Vacuum Applicators and aCustomized Treatment Approach

7. All female subjects of childbearing potential will be asked to take a pregnancy test (urine) prior to being treated. If the subject is pregnant, she will be excluded from participation.

Female subjects of childbearing potential will be advised to avoid becoming pregnant during the course of the study by using a medically accepted form of contraception if they are sexually active. If the subject becomes pregnant during the course of the study, she will not be treated subsequently with the study device or be required to have follow-up photographs and circumference taken. Female subjects of childbearing potential will be assessed for the start date of their last menstrual cycle.

All subjects will be asked to maintain their weight by not making any major changes to their diet or exercise routine during the course of the study. If the weight change is more than 5% of total body weight at 12 weeks after the treatment, the subjects' data will be excluded from the primary effectiveness analyses. Subjects who do not maintain their weight within 5% of total body weight will continue in the study, however their data will be excluded from efficacy analyses.

Subjects who meet all of the inclusion criteria and none of the exclusion criteria shall be eligible to participate in the study and the first treatment will be scheduled.

3.10. Enrollment

Study Candidates who sign the informed consent, meet eligibility criteria and undergo initiation of study treatment are considered enrolled. Study treatment initiation is defined as the initiation of cold therapy after the placement of the applicator on the intended treatment area on the scheduled treatment day.

3.11. Study Treatment

3.11.1. Treatment Visit; Required; Day 0

- 1. Review inclusion and exclusion criteria.
- 2. Administer pregnancy test for female subjects of childbearing potential (urine). Exclude subject from participation if the results are positive.

Part Number: Revision: 01 Page 11 of 28 Title: DualSculpting the Upper Arms Using Vacuum Applicators and a Customized Treatment Approach

- 3. If the subject meets all of the inclusion criteria and none of the exclusion criteria, they will be enrolled in the study and proceed with the treatment.
- 4. Obtain baseline photographs of both right and left arms using the standardized setup and settings. Photos will be taken of each arm from the front and the back.
- 5. Obtain weight.
- 6. Mark the intended treatment areas.
- 7. Optional ultrasound measurements of the fat layer in each upper arm may be obtained using a standardized ultrasound fat measurement protocol.
- 8. Optional caliper measurements of the treatment areas may be obtained.
- 9. Optional circumference measurements of the upper arms may be obtained.
- 10. Determine arm to be treated first based on randomization scheme.

- 16. The subject's level of comfort will be assessed during treatment using a standard scale of 0-10, 0 being no pain and 10 being worst pain imaginable. If discomfort is intolerable, the treatment will be discontinued until the subject is comfortable and treatment, at the discretion of the investigator, can be resumed. Discomfort that results in either a temporary or permanent cessation of the treatment is to be documented as an adverse event.
- 17. Assess for sensory/motor alteration (such as numbness, tingling in hands/fingers) outside of the treatment area. If present, reposition subject and/or applicator. Reapply applicator as needed.
- 18. At the conclusion of the treatment, the investigator or designated staff member will examine the treatment site for any epidermal, dermal or subcutaneous findings (e.g., blanching, erythema, bruising, swelling); alterations in sensation (e.g., numbness, tingling) and pain score will be assessed. The subject will be assessed for any sensory alteration outside of the treatment area.
- 19.

ZELTIQ P/N: Protocol Number: ZA16-005

Part Number: Revision: 01 Page 12 of 28 Title: DualSculpting the Upper Arms Using Vacuum Applicators and a Customized Treatment Approach

- 20. At the investigator's discretion, an additional cooling cycle may be delivered to cover the treatment area (up to two cycles per each upper arm). For additional cooling cycle, repeat steps 12 through 19.
- 21. Repeat steps 11 through 20 on the contralateral arm. Treatments may be concurrently on each arm or consecutively.

The need for post-treatment care is not expected for this study. Subjects will be encouraged to call the study site if they experience any unexpected effects (e.g., severe discomfort, severe and/or prolonged erythema, bruising, swelling; blistering, etc.) which may be related to the study.

3.12. Follow-up Procedures

3.12.1. One-Week Follow-Up Contact; Required: (Day 7 +/- 3 days)

Clinical site staff will contact (via phone or email) subjects one week after treatment for assessment of the treatment areas, pain score, and adverse events. Subjects will be assessed for any sensory alteration outside of the treatment areas. If there are any observations reported, the study site should obtain a resolution date of the symptoms. If there is evidence that an adverse event may have occurred, the subject may be asked to come in for a visit so an appropriate evaluation can be done.

3.12.2. Four-week Follow-Up Evaluation; Required (Day 28 +/- 7 days)

The following evaluations will be performed at the 4-week follow-up visit:

- 1. Obtain weight.
- 2. Obtain photos of both treated arms using the same standardized setup and settings as the pre-treatment photographs (optional).
- 3. Perform clinical assessment of the treatment areas. Evaluate for any epidermal, dermal and subcutaneous findings (e.g., erythema, bruising, swelling, pigment changes) as well as alterations in sensation (e.g., numbness, tingling). Assess for sensory alteration outside of the treatment areas.
- 4. Assess for adverse events.

ZELTIQ P/N:

3.12.3. Twelve-Week Follow-Up Evaluation; Required (Day 84 +/- 14 days)

The following evaluations will be performed at the 12-week visit.

- 1. Obtain weight.
- 2. Obtain photos of both treated arms using the same standardized setup and settings as the pre-treatment photographs.
- 3. Optional ultrasound measurements of the fat layer in each upper arm may be obtained using a standardized ultrasound fat measurement protocol.
- 4. Optional caliper measurements of the treatment areas may be obtained.
- 5. Optional circumference measurements of the upper arms may be obtained.
- 6. Perform clinical assessment of each of the treatment areas (right and left upper arms). Evaluate for any epidermal, dermal and subcutaneous findings (e.g., erythema, bruising, swelling, pigment changes) as well as alterations in sensation (e.g., numbness, tingling). Assess for sensory alteration outside of the treatment areas.
- 7. Administer subject satisfaction questionnaire.
- 8. Assess for adverse events.

3.12.4. Optional Follow-Up Evaluations (up to 4 within study period)

The full evaluation is not required at optional follow-up visits; the extent of the assessment will be at the discretion of the investigator.

Table 3 summarizes study schedule and events at each visit.

Study Task	Screening Visit (< 1 hr)	Treatment #1 (= 3 hrs)</th 1-Week Follow- Up (< 1/2 hr)	4-Week Follow-up (<1/2 hr)	12-Week Follow- up (<1 hr)	Optional Follow- Up*	1-Week Follow- Up (< 1/2 hr)	4-Week Follow-up (<1/2 hr)	12-Week Follow- up (<1 hr)	Optional Follow- Up*
	Day -60 to 0	Day 0	(+/- 3 days)	(+/- 7 days)	(+/- 14 days)	Open
Informed Consent	Х					
Eligibility Criteria	Х	Х				
Pregnancy Test		Х				
Medical History	Х					
Clinical Assessment	Х	Х		Х	Х	
Height	Х					
Weight	Х	Х		Х	Х	

 Table 3. Study Schedule

ZELTIQ P/N:

Part Number:Revision: 01Page 14 of 28Title: DualSculpting the Upper Arms Using Vacuum Applicators and aCustomized Treatment Approach

Photography	X**	Х		X**	Х	
Ultrasound (optional)		Х			Х	
Caliper Measurement (optional)		Х			Х	
Circumference Measurement (optional)		Х			Х	
Treatment		Х				
Pain Assessment		Х	Х	Х	Х	
AE Assessment		Х	Х	Х	Х	
Subject Questionnaire					Х	

*Investigator discretion as to extent of follow-up assessment for optional visits.

**Photography is optional at 4-week visit.

3.13. Assessments

Study-related assessments are described below.

3.13.1. Safety Assessments

The primary safety endpoint is the rate of device- or procedure-related adverse events 12 weeks post-final treatment. Safety will be monitored by documentation of adverse events and clinical assessment of the treatment sites. Post-treatment sensory changes outside of treatment areas will also be documented and assessed.

3.13.2. Photography

A series of baseline and follow-up photographs of the treatment areas will be taken using standardized set up, lighting, and camera settings to ensure consistency. The subject's faces will not be on the photographs. No other identifiable subject information will be recorded on the photographs. The photographs may be cropped or re-sized for comparison purposes but otherwise will not be re-touched or altered in any way. Image files will be stored electronically by ZELTIQ and indexed by subject identifier. Copies of subject photographic data will be filed at the clinical site.

Photos will be reviewed by a blinded independent panel of physician reviewers with expertise in the areas of dermatology and/or plastic surgery. All photographs will be blinded by removing the subject identification and dates of the photographs. The reviewers will be presented with two series of photographs for each treatment area, the pre-treatment and the post-treatment series, and asked to select the series representing the pre-treatment photographs. The order in which the photographs are presented will be randomized by subject. The order in which the pre- and post-treatment series

ZELTIQ P/N: Protocol Number: ZA16-005

This document and the contents hereof are considered proprietary and confidential information of ZELTIQ Aesthetics, Inc. Disclosure to unauthorized individuals or dissemination, publication or copying is prohibited without prior written consent of ZELTIQ.

Part Number:Revision: 01Page 15 of 28Title: DualSculpting the Upper Arms Using Vacuum Applicators and aCustomized Treatment Approach

are presented will also be randomized. The reviewers will be asked to select the baseline photograph series for each treatment area and record their data on individual data collection forms provided by the Sponsor.

3.13.3. Optional Ultrasound Measurement

Ultrasound images may be collected pre-treatment and at each specified follow-up time point. The images will be collected by a qualified representative of the sponsor or site personnel.

arm ultrasound data will be filed at the clinical site. Standardized techniques of obtaining images will be used to ensure consistency throughout the study.

3.13.4. Optional Caliper Measurement

Caliper measurements of the treatment areas may be taken at pre-treatment and at 12-weeks post final treatment. After the treatment area is identified and marked, the thickness of fat layer will be measured using a caliper at the middle of the fat bulge. For each treatment area, three (3) measurements will be taken and recorded.

3.13.5. Optional Circumference Measurement

Circumference data may be collected pre-treatment and at 12-weeks post-treatment.

Part Number: Revision: 01 Page 16 of 28 Title: DualSculpting the Upper Arms Using Vacuum Applicators and a Customized Treatment Approach

3.13.6. Subject Satisfaction

Subject satisfaction data will be collected via a written questionnaire at the final 12-week follow-up visit.

3.14. Endpoints

The objective of this study is to evaluate the safety and efficacy of the CoolSculpting System for non-invasive subcutaneous fat reduction in the upper arms.

3.14.1. Primary Endpoints

The primary endpoints of the study will be defined as follows:

- Safety endpoint: incidence of device- or procedure-related adverse events
- Efficacy endpoint: Correct identification of pre-treatment vs. 12-week post-final treatment images by two out of three blinded independent reviewers. Success will be defined as at least 70% correct identification of the pre-treatment images.

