3.15. Statistical Analysis Plan

3.15.1. Statistical Methods: Overall Plan

Data will be summarized based on the nature of the data. Dichotomous (e.g., gender, independent photographic review) and ordinal (e.g., Fitzpatrick Skin type) data will be tabulated by category. The mean, standard error, maximum and minimum will be tabulated for continuous data (e.g., age,). The significance level will be two-sided 0.05 for all statistical tests.

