3.15.3.2. Primary Efficacy Endpoint: Photographic Evaluation

The primary efficacy endpoint is the correct identification of pre- vs 12-week post-treatment images. Since weight change will affect the image, the analysis will be based on the evaluation of the PP population, i.e. treated subjects followed for 12 weeks who did not became pregnant, and with weight change of no more than 5% at the 12-week visit.

3.15.3.3. Other Assessments:

Subject Satisfaction

The number and percentage of subjects will be summarized for each possible point grade of the satisfaction questionnaire at 12 weeks. The percentage of subjects with satisfied or very satisfied responses will be provided, and the corresponding exact 95% confidence interval (per binomial distribution) will be calculated. The percentage and the exact 95% confidence interval of

Part Number: Revision: 01 Page 18 of 28 Title: DualSculpting the Upper Arms Using Vacuum Applicators and a Customized Treatment Approach

dissatisfied responses (dissatisfied or very dissatisfied) will also be calculated.

Other Assessments of Fat Reduction

Fat reduction may be assessed using other various methods, which may include; ultrasound, caliper and circumference measurements.

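### The primary efficacy rule is a bare observed rate of at least 70%, with no interval, no comparison with 50% guessing, and no statement of whether arms or subjects are counted

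*Combined protocol and SAP*

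**What the plan says.** The Protocol Summary (section 1) defines the endpoint as "Correct identification of pre-treatment vs. 12-week post-final treatment images by at least two out of three blinded, independent reviewers". Section 3.14.1 repeats the two-of-three rule and adds the criterion "Success will be defined as at least 70% correct identification of the pre-treatment images".

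Section 3.13.2 describes the reading task: "The reviewers will be presented with two series of photographs for each treatment area", one from before and one from after treatment, in randomized order, and "The reviewers will be asked to select the baseline photograph series for each treatment area". Section 3.12.3 identifies the treatment areas as the right and left upper arms. Treatment is bilateral (section 2.2), and at most 15 subjects are treated (section 3.6).

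On analysis, section 3.15.1 says "Dichotomous (e.g., gender, independent photographic review) and ordinal (e.g., Fitzpatrick Skin type) data will be tabulated by category" and "The significance level will be two-sided 0.05 for all statistical tests". Section 3.15.3.2 says "The primary efficacy endpoint is the correct identification of pre- vs 12-week post-treatment images" and restricts the analysis to the per-protocol population, which section 3.15.2 defines by subject. It names no test, interval, reference value or counting unit. For satisfaction, which is not a primary endpoint, section 3.15.3.3 does specify precision: "the corresponding exact 95% confidence interval (per binomial distribution) will be calculated".

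**The concern.** A forced choice between two series has a built-in floor: with no visible treatment effect, half the answers are still right. A rate of 70% means something only in relation to that 50% and to the number of independent results behind it. The plan does not mention the 50%, asks for no measure of precision, and leaves the unit open: photographs are read by arm, while the analysis population is defined by subject.

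The primary efficacy conclusion is at stake. The rule, followed exactly, can declare success on data that guessing could readily produce, and nothing in the planned output would show it. A reader could work out the interval from a tabulated count of subjects, but not from a count of arms, because the tabulation does not show how right and wrong arms pair within subjects.

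**Working it through.** The plan gives no power, error-rate or sample-size calculation, so there is no figure to reproduce.

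**Inputs.** Threshold 70% (3.14.1); two-of-three majority (sections 1 and 3.14.1); two-way choice per arm (3.13.2); at most 15 subjects and so 30 arms (3.6, 2.2); two-sided 0.05 (3.15.1).

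**1. Guessing rate.** One guess is right with probability 0.5. A majority of three independent guesses is right with probability 3(0.5)³ + (0.5)³ = 0.5. This follows from the design; the plan does not state it.

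**2. Formulas.** The minimum pass k is the smallest whole number at or above 0.7n. The exact two-sided p against 0.5 is 2·P(X≥k | n, 0.5). The Clopper-Pearson limits L and U solve P(X≥k | n, L) = 0.025 and P(X≤k | n, U) = 0.025.

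**3. Arms counted, treated as independent.**
- 15 subjects: 21/30, 50.6% to 85.3%, p = 2 × 0.0214 = 0.043.
- 14 subjects: 20/28, 51.3% to 86.8%, p=0.036.
- 13 subjects: 19/26, 52.2% to 88.4%, p=0.029.
- 12 subjects: 17/24, 48.9% to 87.4%, p=0.064.
- 10 subjects: 14/20, 45.7% to 88.1%, p=0.12.

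The minimum pass excludes 50% with 13 to 15 subjects and not with 5 to 12.

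**4. Arms counted, pairing kept.** Let b, s and w be the numbers of subjects with both arms right, one right, and both wrong. At 21/30, b+s+w=15 and 2b+s=21, so b=6+w and s=9−2w. The sign test compares b with w. A cluster interval uses each subject's mean (1, 0.5 or 0): 0.70 ± 2.145·√[(0.09b+0.04s+0.49w)/(14×15)], where 2.145 is the t quantile on 14 degrees of freedom.

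| b / s / w | sign test p | cluster 95% interval |
|---|---|---|
| 6 / 9 / 0 | 0.031 | 56.0% to 84.0% |
| 7 / 7 / 1 | 0.070 | 52.5% to 87.5% |
| 8 / 5 / 2 | 0.109 | 49.6% to 90.4% |
| 9 / 3 / 3 | 0.146 | 47.1% to 92.9% |
| 10 / 1 / 4 | 0.180 | 44.8% to 95.2% |

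The same 21/30 excludes chance by the sign test only if no subject has both arms wrong. In the 7/7/1 case the interval and the test disagree.

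**5. One two-way result per subject.**
- n=15: 11/15. P(X≥11) = (1365+455+105+15+1)/32768 = 0.059, so p=0.12; interval 44.9% to 92.2%.
- n=10: 7/10. P(X≥7) = (120+45+10+1)/1024 = 0.172, so p=0.34.
- Over n=5 to 15, the highest lower limit at the minimum pass is 46.2% (10/13).
- 12/15 does exclude 50% (51.9% to 95.7%, p=0.035).

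Guessing alone thus meets the rule in 5.9% of studies at n=15 and 17.2% at n=10. The per-protocol number can fall below 15 through weight change over 5%, pregnancy, incomplete treatment or loss to follow-up (3.9.1, 3.15.2, 3.15.3.2).

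**The case against.** The strongest reply is that this is a single-center, non-randomized cohort of at most 15 subjects with a preset descriptive goal, and that the plan never says a 70% pass shows better-than-guessing identification. That is true, and it is why the 70% rule should stay. But section 3.14 gives the objective as evaluating efficacy, and section 3.14.1 declares a primary endpoint with a success criterion. A declared success needs its uncertainty shown, as the plan already does for satisfaction.

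A second reply is that the reading unit is the arm, and that at full enrolment 21/30 does exclude 50%. This stands under independence with 13 to 15 subjects. It fails with 12 or fewer, and with 15 subjects it fails in four of the five possible pairings once arms are kept together.

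A reader might go further and infer that individual readings are a third possible denominator. The documents do not support that: the two-of-three rule already combines the three readings into one result. A reader might also score a subject as correct only when both arms are, and show a pass turning into a fail on the same data. No such rule appears in the documents. Nor do they say how one result per subject would be formed from two arms, so the per-subject figures hold only if each subject gives a single two-way result.

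**Conclusion.** The point holds and should be fixed. As written, the success rule can be met by a result compatible with guessing, and the plan does not ask for the analysis that would show it. How serious this is depends on the missing unit. Counting arms, a minimum pass is borderline at full enrolment and inadequate with 12 or fewer subjects. Counting one two-way result per subject, it never excludes 50% for n from 5 to 15.

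A reader might infer that the 70% rule can never separate treatment from chance. That is too strong: results above the minimum, such as 12/15, do exclude 50%, and so can 21/30 arms with favorable pairing.

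The conclusion assumes a 50% guessing rate, which follows from the two-way choice, and the stated two-sided 0.05. The degree of correlation between a subject's arms is not given in the documents.

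**What to change.** In section 3.15.3.2:

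1. Keep the 70% rule and state whether it counts arms or subjects.
2. Report that same rate with a two-sided 95% interval beside the 50% reference, and one named test against 50% at two-sided 0.05.
   - If each subject gives one two-way result: exact binomial test and Clopper-Pearson interval.
   - If arms are counted: an interval for the arm-level rate with the subject as the cluster (for example, from each subject's mean of 0, 0.5 or 1), and the exact sign test on subjects, both right against both wrong. Report split subjects. Label any interval for untied subjects as a different proportion from the arm-level rate.
3. Because the cluster interval and the sign test can occasionally disagree, name the test as decisive.
4. Do not describe a 70% pass as better than guessing unless that test excludes 50%.

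The cost is a short addition to the SAP text and no new data. The downside is that a threshold-level success may be reported with an interval that includes chance. At an assumed true rate of 80% (not in the documents) and n=15 subjects, 83.6% of studies meet the 70% rule and 64.8% also exclude 50%, so this happens in 83.6% − 64.8% = 18.8%, about 19%. At assumed true rates of 70% and 90% it is 22% and 4%. The sign test also sets aside subjects with one arm right and one wrong. Making exclusion of 50% a formal condition of success would be a separate choice for the sponsor and is not part of this change.
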